13.3.4.5 Peak Left Ventricular Global Longitudinal Strain (GLS)

Speckle tracking echocardiography (STE) for measurement of peak left ventricular GLS should be performed at each study interval. Serial exams for each subject should be performed using the same vendor's equipment and software to the extent practical. The following is intended to provide a standardized approach for image acquisition and minimize sources of variability.

Optimal Image Acquisition (Figure 12)

- **Electrocardiographic (ECG) gating.** An optimal ECG signal with prominent P, R, and T waves and minimal heart rate variability should be present across 3 cardiac cycles in patients with normal sinus rhythm. Clips for GLS should include 3 cardiac cycles.
- **Frame rate.** Images for STE should be maintained at a frame rate of 40 to 90 frames per second through optimization of image depth and sector width. Images for GLS should be acquired at the same depth and section width.
- **Image quality.** Images should be acquired using optimal gain settings and breath-hold techniques to delineate endocardial and epicardial borders throughout the cardiac cycle and to avoid artifact related to excess noise, rib or lung movements, and translational motion of the heart. Images should be "on-axis", with image width and depth focused on the LV. It is essential to avoid foreshortening in the apical views. Also, there should be a space of at least 5 mm between the epicardium in diastole and the sector width.⁷²
- **Required views.** The following views are required for GLS: 1) apical 2 chamber, 2) apical 3 chamber (apical LAX), and 3) apical 4 chamber. It is recommended the images for GLS analysis be acquired at the beginning or end of the apical section of the exam; this allows the operator to see the apical images in a row and facilitates selection of images with similar heart rates.

[figure not shown]

Figure 12. Example of optimal apical 2,3, and 4 chamber images for GLS analysis. Endocardial borders are visualized over the cardiac cycle, apex not foreshortened, frame rate is 50 fps, and depth and sector width the same in all three.

Image Analysis and Post-Processing

Contemporary echocardiography systems perform automated analysis of GLS once the required apical views have been selected, however the automated analysis for each of the views should be visually assessed for the following and corrected if indicated.

Region of interest (Figure 13). The auto-generated region of interest (ROI) for each view should be visually assessed for adequacy of tracking. The ROI should encompass the myocardium from the subendocardial border to the subepicardium border⁸¹, and should be at least 85% to 90% of the thickness of the myocardium.⁷² If the auto-generated ROI is inadequate, it should be adjusted manually or semi-automatically using the “3 point” method available on contemporary systems. The redrawn ROI should be visually assessed, and the endocardial borders and ROI width adjusted as needed. The ROI should include the endocardium and myocardium within the lines, excluding the pericardium, trabeculation, and papillary muscles.

[figure not shown]

Figure 13. Three-point method for defining start and end points for ROI. For the apical 2-chamber view, the first point is on the basal posterior wall at the mitral annulus, the second point is at the basal anterior wall at the mitral annulus, and the third point is at the apex. For the apical 3-chamber view, one point is placed at the basal posterior wall at the mitral annulus (ventricular side), one point is placed at the apex, and one point is placed at the base of the anterior septum just proximal to the LVOT. For the apical 4-chamber view, the first point is placed on the basal inferoseptum at the mitral annulus (ventricular side), the second point is placed at the basal anterolateral wall at the mitral annulus (ventricular side), and the third point is at the apex.

Event timing. The apical 3 chamber view should be reviewed frame by frame to ensure the reference point for defining aortic valve closure (AVC) is correct. AVC should be corrected manually if indicated.

Review of Strain Curves. The resulting strain curves and bulls-eye plot should be reviewed for possible errors in tracking and the affected analyses corrected as indicated. The final peak average LV GLS should be reported on the eCRF.

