13.3.2 General Procedures

- Protocol-driven exams should be performed by designated individuals delegated by the site PI
- Subject's blood pressure and weight should be recorded at each visit. Blood pressure should be taken with the subject sitting in a chair after resting for 5-10 minutes. Subject's weight can be taken with shoes off or on.⁶
- The subject's ID number and exam interval should be annotated on the image.
- A simultaneous ECG with a clearly defined R-wave should be displayed on all clips
- Digital cine clips should be a minimum of two cardiac cycles
- To minimize inter-vendor and inter-software variation in GLS measurements, serial assessments should be performed using the same vendor's equipment and software to the extent practical.
- Color Doppler images for assessment of prosthetic regurgitation should be obtained at a minimum frame rate of 20 Hz through optimization of sector width and depth settings.
- Still frames of measured variables should be captured. In addition, still frames of spectral Doppler tracings without the measurements should be captured to facilitate analysis by the Echo Core Lab. Still frames of spectral and tissue Doppler tracings should contain a minimum of 3 cardiac cycles for subjects in sinus rhythm, and a minimum of 5 cardiac cycles for subjects in atrial fibrillation (two sequential frames per variable may be necessary).
- Spectral and tissue Doppler waveforms should be recorded at a minimum sweep speed of 50 mm/sec.
- Exams will be transmitted to the Echo Core Lab via web-based picture archiving and communication system. Details of the image transmission process for each site will be established during site initiation process.

⁶ Weight can be taken from the clinical assessment exam. Blood pressure should be taken within 5-10 minutes before or after the echo exam.

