13.3.5 Echocardiography Core Lab Analysis

Protocol-required and endpoint or event related (as applicable) echocardiograms will be sent to the ECL for assessment: the data generated by the ECL will be the primary data used for analysis and reporting. Received echocardiograms will be logged in and analyzed by the ECL according to their procedures determined for this study. Qualitative assessment of valvular regurgitation and quantitative analysis of variables related to hemodynamic valve performance, cardiac function and cardiac dimensions will be performed according to the methods described in Section 13.3.2.

The ECL will report the following variables:

- Height (cm) and weight (kg)
- Heart rate (HR)
- Left ventricular outflow tract (LVOT) diameter in mid systole
- Max aortic or prosthetic valve velocity (vMax) by CW Doppler
- Aortic or prosthetic valve velocity time integral (VTI) by CW Doppler
- Mean gradient across aortic or prosthetic aortic valve (MG) by CW Doppler
- LVOT VTI by PW Doppler
- Systolic ejection time (ET)
- Grade of native aortic regurgitation (baseline only)
- Grade of prosthetic paravalvular regurgitation (post-implant only)
- Grade of prosthetic transvalvular regurgitation (post-implant only)
- Right ventricular outflow tract (RVOT) diameter (post-implant; if AR > mild by visual estimate)
- RVOT VTI (post-implant; if aortic regurgitation > mild by visual estimate)
- Grade of prosthetic total (transvalvular plus paravalvular) regurgitation (post-implant only)
- Grade of mitral regurgitation (MR)
- Grade of tricuspid regurgitation (TR)
- Max TR jet velocity (if TR is present)
- Left ventricular internal dimension at end diastole (LVIDD)
- Left ventricular internal dimension at end systole (LVIDS)
- Interventricular septal thickness at end diastole (IVS)
- Left ventricular posterior wall thickness at end diastole (LVPW)
- Left ventricular end diastolic volume by modified Simpson's rule (LVEDV)
- Left ventricular end systolic volume by modified Simpson's rule (LVESV)
- Left atrial volume at end systole by bi-plane Simpson's rule (LAV)
- Left atrial internal linear dimension at end systole (LA)
- Mitral inflow early (E) velocity
- Mitral inflow atrial (A) velocity
- Mitral inflow E wave deceleration time (MdT)
- Mitral annular early (e') diastolic velocity; lateral
- Mitral annular late (a') diastolic velocity; lateral
- Mitral annular early (e') diastolic velocity; medial

- Mitral annular late (a') diastolic velocity; medial

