- Grade of diastolic dysfunction
- Pattern of LV geometry
- Peak average left ventricular global longitudinal strain (GLS) measured at end systole (aortic valve closure)
- Vendor, model, and software version of echocardiography system
- Tricuspid annular plane systolic excursion (TAPSE)
- Basal right ventricular linear dimension at end diastole (RVD)
- Right ventricular area at end diastole (RVAD)
- Right ventricular area at end systole (RVAS)

In addition, the following variables will be derived by the central database from the appropriate measurements reported by both the site and ECL.

- **Body Surface Area (BSA) in m²**
BSA = $0.007184 \times \text{height} \times \text{weight} \times 0.425$
Where: BSA is the body surface area in cm², height is in cm, and weight is in kg⁸
- **Body Mass Index (BMI) in kg/cm**
BMI = weight in kg/height in cm
- **Aortic Valve Area (AVA) in cm²**
AVA = LVOT diameter in cm² x 0.785 x (LVOT VTI/aortic valve VTI)
Where: LVOT VTI is the velocity time integral of the left ventricular outflow tract in cm, and aortic valve VTI is the velocity time integral of the native aortic valve in cm
- **Aortic Valve Area Index (AVAI) in cm²/m²**
AVAI = AVA/BSA
Where: AVA is the native aortic valve area in cm², and BSA is the body surface area in m²
- **Effective Orifice Area (EOA) in cm²**
EOA = LVOT diameter² x 0.785 x (LVOT VTI/Aortic valve VTI)
Where: LVOT VTI is the velocity time integral of the left ventricular outflow tract in cm, and aortic valve VTI is the velocity time integral of the aortic prosthesis in cm
- **Effective Orifice Area Index (EOAI) in cm²/m²**
EOAI = EOA/BSA
Where: EOA is the effective orifice area in cm², and BSA is the body surface area in m²
- **Doppler Velocity Index (DVI)**
DVI = LVOT VTI/Aortic valve VTI
Where: LVOT VTI is the velocity time integral of the left ventricular outflow tract in cm, and aortic valve VTI is the time velocity integral of the prosthetic aortic valve in cm

⁸ Height will be pulled from the site baseline eCRF, and weight will be pulled from the site eCRF for the visit

- **Estimated Right Ventricular Systolic Pressure (RVSP) in mmHg**
 $RVSP = (4 \times MVTR \text{ jet}^2) + 10$
Where: MV TR jet is the max velocity of the tricuspid regurgitant jet, and 10 = the assumed mean right atrial pressure in mmHg
- **Cardiac Output (CO) in l/min**
 $CO = (SV \times HR)/1000$
Where: SV is the stroke volume in ml/beat, and HR is the heart rate in beats per minute
- **Cardiac Index (CI) in l/min/m²**

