The primary objectives of this feasibility study are as follows:

1. Characterize the spectrum of cardiac function, symptomology, and severity of aortic stenosis in the study populations,
2. Estimate event rates for potential safety and effectiveness endpoints to be evaluated in pivotal studies for the proposed patient populations, and
3. Evaluate the effect of TAVR on cardiac function, functional capacity, effort tolerance, and patient-reported quality of life in the study populations.

The study objectives and associated endpoints are intended to fully characterize the spectrum of aortic stenosis (AS) severity, left ventricular (LV) function, and symptomology of patients with moderate

symptomatic and severe asymptomatic AS, provide information on event rates for pivotal sample size estimations, and refine the entrance criteria for future pivotal studies. The full list of protocol defined endpoints are detailed in Section 7.9. Of the protocol defined endpoints, the following key study endpoints have been identified:

Key Safety Endpoints:

- All-cause mortality at 30 days and 6 months
- All stroke (disabling and non-disabling) at 30 days and 6 months
- Valve-related dysfunction requiring repeat procedure at 30 days and 6 months
- New permanent pacemaker implant (PPI) at 30 days and 6 months

Key Efficacy Endpoints:

- Cardiovascular and heart failure hospitalizations at 30 days and 6 months
- Heart failure events at 30 days and 6 months
- Change in Kansas City Cardiomyopathy Questionnaire (KCCQ) at 6 months
- Change in Six-Minute Walk Test (6MWT) at 6 months
- Change in cardiac function by echo (LVEF, Peak GLS, E:e') at 6 months

5. Investigation Plan

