7.9.2.9 Change in peak global longitudinal strain (GLS) from baseline at 6 months

Peak global longitudinal strain (GLS) will be analyzed according to the data collected on the core lab echo CRF. At each time point, peak GLS will be summarized descriptively as continuous data. Change from baseline will be summarized descriptively along with two-sided 95% confidence interval and p-value from a paired t-test. The endpoint will be analyzed using the Implanted set.

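### The SAP analyses change in peak GLS on all pairs without using the recorded vendor and software field, so a platform offset running mainly one way could be mistaken for a TAVR effect

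*Protocol*

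**What the plan says.** SAP Section 4 lists among the key efficacy endpoints "Change in cardiac function by echo (LVEF, Peak GLS, E:e') at 6 months". SAP 7.9.2.9 gives the data source and method: "Peak global longitudinal strain (GLS) will be analyzed according to the data collected on the core lab echo CRF" and "Change from baseline will be summarized descriptively along with two-sided 95% confidence interval and p-value from a paired t-test". The population is every implanted subject with data: "The endpoint will be analyzed using the Implanted set".

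Protocol 13.3.2 asks for serial use of one system and gives the reason: "To minimize inter-vendor and inter-software variation in GLS measurements". Protocol 13.3.4.5 repeats the request, again without making it mandatory: "Serial exams for each subject should be performed using the same vendor's equipment and software to the extent practical". Sites use their own echocardiography equipment (Protocol 6.12), at up to 25 centers.

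The information needed to identify a change of system is recorded. Protocol 13.3.3 (site) and 13.3.5 (core lab) both list "Vendor, model, and software version of echocardiography system". Protocol 13.3.5 also says of the core lab that "the data generated by the ECL will be the primary data used for analysis and reporting".

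**The concern.** The endpoint is a before/after difference with no control arm, so anything that changes between the two exams enters the estimate together with the treatment. The protocol names one such thing, the measuring platform, and collects the variable that would reveal it. The SAP does not use that variable: not in 7.9.2.9, not under missing and spurious data (7.4), and not in the subgroup section (7.9.4). No count of pairs with different systems is planned, and neither is a same-platform analysis.

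The study is meant to inform pivotal trials, and GLS is both a key outcome and a planned subgroup variable. A platform offset could create an apparent change in GLS or hide a real one, and the planned output would not let a reader tell.

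**Working it through.** **1. Is there a figure to reproduce?** No. SAP Section 6 says the 75 was not obtained by a sample size calculation, and neither document gives an SD or expected change for GLS. Everything numerical below rests on assumed inputs.

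**2. How far apart can the paired exams be?** Baseline falls within 12 weeks before submission to the eligibility committee (Protocol 6.6). TAVR should follow within 90 days of approval (Protocol 6.5), and the 6-month window closes at day 210 (Protocol 6.6). That is up to 84 + 90 + 210 = 384 days, plus the committee's review time. A diagnostic echocardiogram done before consent may also serve as baseline (note to Figure 2), so it may precede the study's instructions. A change of system within a pair is therefore possible. The documents do not say how often it will happen.

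**3. Bias formula.** Let f be the share of pairs read on different platforms and b the offset in strain points, with the same sign in every such pair. With no true change:

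- expected mean change = f × b
- SE ignoring the extra spread = SD/√n
- SE including it = √(SD² + f(1 − f)b²)/√n

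**4. Numbers.** Assumed: SD of change 2.5 points and n = 75, so the simple SE is 2.5/√75 = 0.29.

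| f | b | Bias f × b | Bias / simple SE | SE with extra spread | Bias / that SE |
|---|---|---|---|---|---|
| 10% | 1 | 0.1 | 0.35 | √(6.25 + 0.09)/√75 = 0.29 | 0.34 |
| 20% | 2 | 0.4 | 1.4 | √(6.25 + 0.64)/√75 = 0.30 | 1.3 |
| 30% | 3 | 0.9 | 3.1 | √(6.25 + 1.89)/√75 = 0.33 | 2.7 |

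**5. Chance of p < 0.05 with no true change** (75 pairs, noncentral t):

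| f | b | SD 2.5 | SD 3.0 | SD 3.5 |
|---|---|---|---|---|
| 10% | 1 | 6% | 6% | 6% |
| 20% | 2 | 26% | 20% | 16% |
| 30% | 2 | 49% | 37% | 29% |

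Simulation with 40,000 runs at SD 3.0 gave 19% and 35% for the second and third rows.

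**6. Does direction matter?** Yes. With about 30% of pairs switched and 2-point offsets split evenly between the two signs, the simulated mean bias was about 0 and the rejection rate about 4%. Only a predominantly one-way offset produces a false effect.

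**7. What restriction to same-platform pairs does.** The platform bias is removed and the simulated rejection rate returns to about 5%. The price is precision. At SD 3.0 the 95% half-width is 0.69 with 75 pairs, 0.77 with 60 (20% mismatched), 0.83 with 53 (about 30%) and 1.00 with 37 (about 50%).

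**The case against.** The strongest reply is central reading. The endpoint is the core lab's GLS, not the site's (Protocol 10.5 and 13.3.5; SAP 7.9.2.9). The core lab works to procedures that these documents do not reproduce. If it reads all visits on one strain package, upgrades to site strain software do not reach the endpoint. That stands as a possibility. However, nothing in either document says that one fixed package is used. Protocol 13.3.5 refers for methods to 13.3.2, where the soft same-vendor request sits. A fixed package would also leave any difference due to the acquiring vendor.

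Second, nothing shows that mismatched pairs will occur. The same-system request is made twice, and exams should be done at the study site. This is fair: the point concerns an unguarded risk, not an observed fault.

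Third, a reader might infer that because upgrades run from old to new, the offset must be systematic and share one sign. The documents do not support that. Order in time does not fix the sign of the strain offset, and up to 25 sites may use different vendors. A reader might also take the 3.1 SE corner as the likely size. It combines both worst cases, omits the extra spread (2.7 SE with it) and supposes 75 evaluable pairs.

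Fourth, the study is descriptive and SAP 7.9.4 allows further subgroup analyses, so the table could be produced without a plan change. True, but an analysis chosen after seeing the data carries less weight than one named in advance.

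**Conclusion.** The point holds as a conditional risk and a low-cost improvement, not as an error in the plan. It needs three things together: some pairs on different platforms, core lab reading that does not neutralise the difference, and offsets mainly in one direction. The documents settle none of the three. Under the assumed values the bias runs from negligible (10% of pairs, 1 point) to about 0.4 points, or 1.3 to 1.4 SE (20%, 2 points). Larger values need more extreme inputs.

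Because the study has no formal hypotheses, the harm would be a misleading estimate and p-value carried into pivotal planning, not a failed test. A reader might also infer that GLS is a declared pivotal entry criterion. The protocol speaks only of additional markers of LV dysfunction (Section 3.1), and the SAP uses baseline GLS as an exploratory split.

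**What to change.** In SAP 7.9.2.9:

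- Keep the all-pairs analysis as written.
- Report the number of baseline/6-month pairs with a different vendor or software version.
- Prespecify a sensitivity analysis of change in GLS in same-platform pairs, meaning the same vendor and the same strain software used for the reading.
- Show both estimates with their confidence intervals side by side, and qualify the GLS conclusion by the same-platform result. This avoids a rule that depends on judging, after the fact, whether the two results differ.

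State the core lab's policy on strain software and version as well. The recorded field describes the echocardiography system, so the package used for the reading may have to be confirmed with the core lab.

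The cost is one extra table, mostly from data already collected, and a wider interval in the matched set: for example, a half-width of 0.77 instead of 0.69 if 20% of pairs are mismatched, at an assumed SD of 3.0. If about half were mismatched it would be 1.00, which is a further reason to keep the all-pairs result beside it.

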13.3.4.6 Left Ventricular Diastolic Function

A spectral Doppler recording of mitral inflow should be obtained with PW Doppler in the apical 4-chamber view, using a 1 to 2 mm sample volume placed between the mitral leaflet tips (Figure 14, A). The following variables should be measured:

- Mitral inflow “A” velocity
- Mitral inflow “E” velocity
- Mitral inflow E-wave deceleration time (MdT)

Mitral annular velocities should be recorded from the lateral and medial (septal) aspects of the mitral annulus using tissue Doppler imaging (TDI) in the apical 4-chamber view (Figure 14, C). Minimal angulation (<20 degrees) should be present between the ultrasound beam and the plane of cardiac motion. The following variables should be measured:

- Mitral annular tissue Doppler early diastolic velocity (e'); medial and lateral
- Mitral annular tissue Doppler late diastolic velocity (a'); septal and lateral

[figure not shown]

Figure 14. (A) Apical 4 chamber with sample volume placement between mitral leaflet tips during diastole; (B) Doppler gains and wall filters optimized to clearly show onset and cessation of mitral inflow; (C) A 2 to 5 mm sample volume should be positioned at or 1 cm within the septal and lateral insertion sites of the mitral leaflets and adjusted as necessary to cover the longitudinal excursion of the mitral annulus in both systole and diastole.

13.3.4.7 Prosthetic Aortic Regurgitation

An integrated approach using color flow, pulsed-wave (PW), and continuous-wave (CW) Doppler is used to assess the severity of transvalvular and paravalvular aortic regurgitation (AR). Color flow Doppler imaging should be performed from the parasternal long and short-axis views, and the apical 5-chamber and apical 3 chamber views (Figure 15). The entire valve should be scanned, from the aortic to the ventricular end of the TAV to identify the number, location, and direction of regurgitant jets, which can be multiple and eccentric. In the short axis view, color imaging should be performed at multiple planes (sweeping from level of the leaflets to below the skirt and frame to assess paravalvular regurgitation), and at the coaptation point of the leaflets for transvalvular (central) regurgitation (Figure 16).⁸²

Figure 15. Standard views showing detection of paravalvular regurgitation. Color coding delineates the regions around the valve that can be visualized from the parasternal and apical views. With ultrasound plane rotation, tilting upwards or sideways, a more complete interrogation of the valve can be accomplished. Apical views are important in that some jets may not be detected in the parasternal views because of shadowing from the prosthesis. [Journal of the American Society of Echocardiography 2019 32431-475DOI: (10.1016/j.echo.2019.01.003, Copyright © 2019 American Society of Echocardiography)]

[figure not shown]

Figure 16. Imaging planes for detection for paravalvular and transvalvular regurgitation. Thorough imaging of the entire valve is needed to identify the origin and vena contracta of regurgitant jets, which may be multiple and not be all at the same level. A sweep of the aortic root from the parasternal SAX view is recommended. [Journal of the American Society of Echocardiography 2019 32:431-475 DOI: (10.1016/j.echo.2019.01.003, Copyright © 2019 American Society of Echocardiography)]

If prosthetic AR is seen by color Doppler, a CW spectral Doppler recording of the regurgitant signal should be obtained for measurement of pressure half-time and assessment of jet density (Figure 17, A). In addition, a PW spectral Doppler recording from the proximal descending or abdominal aorta should be recorded to assess the degree of flow reversal (Figure 17, B).

[figure not shown]

Figure 17. (A) CW Doppler spectral recording of AR regurgitant signal and measurement of pressure half-time; (B) PW Doppler spectral recording from abdominal aorta showing flow reversal.

If AR appears more than mild by visual assessment, and if image quality is technically adequate, the RVOT and LVOT diameters and VTIs can be measured to calculate regurgitant volume and fraction (Figure 18).

[figure not shown]

Figure 18. Example of quantification of aortic regurgitant fraction and volume to complement other assessments. Stroke volume is calculated at the RVOT and LVOT.

Grading of Prosthetic Regurgitation. The degree of transvalvular, paravalvular, and total (transvalvular plus paravalvular) AR should be graded as none, mild, moderate, or severe based on overall comprehensive evaluation the echocardiographic findings in Table 17, Figure 19.⁸² The category of “trace” can be used if regurgitation is barely detectable. The following caveats are noted in the ASE 2019 Guidelines for the evaluation of valvular regurgitation after percutaneous valve replacement.

1. Central AR jets will occur at the level of leaflet coaptation whereas PVR will be seen at the proximal (ventricular) edge of the valve. The jet must enter the LV to be considered true regurgitation, thus imaging just below the edge of the stent will confirm the presence of true PVR; however, the vena contracta of the jet should be measured at its narrowest region.
2. Color flow around the TAV within the sinuses of Valsalva but above the annular valve skirt should not be mistaken for PVR. Flow in the sinuses has low velocity and does not connect with the LVOT in diastole. Scanning through the long axis of the valve is useful in distinguishing color flow in the sinuses from PVR.
3. Small jets of regurgitation are typically isolated to open stent cells and not at the “nodes” of the stent frame. It is important not to include the stented frame in the measurement of circumferential extent of the regurgitation but to integrate only the regurgitant jets when determining the circumferential extent.

Table 17. Evaluation of severity of prosthetic aortic regurgitation post TAVR

	Mild	Moderate	Severe
Structural Parameters			
Position of prosthesis	Usually normal	Variable	Frequently abnormal
Stent and leaflet morphology	Usually normal	Variable	Frequently abnormal
Doppler Parameters			
Proximal flow convergence (CD)	Absent	May be present	Often present
AR velocity waveform density (CWD)	Soft	Dense	Dense
Diastolic flow reversal in proximal aorta	Brief, early diastolic	May be holodiastolic	Holodiastolic (end-diastolic velocity \geq 20 cm/sec)
Diastolic flow reversal in abdominal aorta	Absent	Absent	Present
Vena contracta width (cm) (CD)	< 0.3	0.3 – 0.6	> 0.6
Vena contracta area (cm ²) * (2D, CD)	< 0.10	0.10 – 0.29	\geq 0.30
Circumferential extent of PVR (%) [†]	<10	10-29	\geq 30
Jet deceleration rate (PHT, ms) [#] (CWD)	Variable Usually > 500	Variable	Steep
Regurgitant volume (mL)	<30	30-59	>60
Regurgitant fraction (%)	<30	30-49	\geq 50
EROA (cm ²) ^{##}	<0.10	0.10 – 0.29	\geq 0.30

[figure not shown]
CD, Color Doppler; CWD, continuous wave Doppler; PVR, paravalvular regurgitation; PHT, pressure half-time

*Vena contracta area is measured by planimetry of the vena contracta of the jet(s) on the 2-D color Doppler images in the short-axis view

[†]Circumferential extent of PVR best not to be used alone, but in combination with vena contracta width or area

[#]Influenced by LV and aortic compliance

^{##}ERO is infrequently used in A

*	AR after TAVR is frequently eccentric, involving more than one jet; an integrative approach is essential
¶	Regurgitant volume for severe AR may be lower in low flow conditions.
§	EROA is infrequently used in AR. It is derived using the volumetric approach, not PISA.

Figure 19. Suggested algorithm to guide integration of multiple parameters of AR severity after TAVR. Good-quality echocardiography imaging and complete data acquisition are assumed. [Journal of the American Society of Echocardiography 2019 32:431-475 DOI: (10.1016/j.echo.2019.01.003, Copyright © 2019 American Society of Echocardiography)]

